## **2. LIST OF ABBREVIATIONS**

Term	Definition / description
AE	Adverse Event
AESI	Adverse event of special interest
AIC	Akaike Information Criterion
ALT	Alanine aminotransferase
ANCOVA	Analysis of Covariance
AST	Aspartate aminotransferase
ATC3	Anatomical-Therapeutic-Chemical classification level 3
AUC	Area under the curve
[REDACTED]	
BI	Boehringer Ingelheim
BLQ	Below the lower limit of quantification
BMI	Body mass index
[REDACTED]	
CFB	Cystic Fibrosis Bronchiectasis
CFTR	Cystic fibrosis transmembrane conductance regulator
CFTR-MT	Cystic fibrosis transmembrane conductance regulator modulator therapy
[REDACTED]	
CI	Confidence interval
CKD-EPI	Chronic Kidney Disease Epidemiology Collaboration
C max	Maximum measured concentration of the analyte in plasma
COPD	Chronic obstructive pulmonary disease
CRF	Case report form
[REDACTED]	
CTP	Clinical trial protocol
CTR	Clinical trial report
[REDACTED]	
DBL	Database lock
DDR	Data Delivery Request
DNA	Deoxyribonucleic acid
ECG	Electrocardiogram

[figure not shown]
Term	Definition / description
eCRF	Electronic case report form
EDMS	Electronic document management system
eGFR	Estimated glomerular filtration rate
EMA	European Medicines Agency
EoS	End of study
EoT	End of treatment
EudraCT	European Union Drug Regulating Authorities Clinical Trials
	
HR	Hazard ratio
ICE	Intercurrent event
ICH	International Conference on Harmonisation
iPD	Important protocol deviation
	
KM	Kaplan Meier
	
LLN	Lower limit of normal
LLOQ	Lower limit of quantitation
LPLT	Last patient last treatment
MedDRA	Medical Dictionary for Regulatory Activities
min	minimum
MMRM	Mixed model with repeated measurements
NCFB	Non-Cystic Fibrosis Bronchiectasis
NE	Neutrophil elastase
	
PD	Pharmacodynamics
PK	Pharmacokinetics
PKS	Pharmacokinetic parameter set

Term	Definition / description
PN	Preferred name
PT	Preferred term
pt-yrs	patient-years
Q1	First quartile
Q3	Third quartile
REML	Restricted maximum likelihood
REP	Residual effect period
RS	Randomised set
SAE	Serious adverse event
SD	Standard deviation
SE	Standard error
SI	Système international d'unités
SMQ	Standardised MedDRA Query
SOC	System organ class
SS	Screened set
TEAE	Treatment-emergent adverse event
TMF	Trial master file
TS	Treated set
TSAP	Trial statistical analysis plan
ULN	Upper limit of normal range
WHO-DD	World Health Organization – Drug Dictionary

### **3. INTRODUCTION**

[figure not shown]
As per ICH E9 ([9.1](#)), the purpose of this document is to provide a more technical and detailed elaboration of the principal features of the analysis described in the protocol, and to include detailed procedures for executing the statistical analysis of the primary and secondary variables and other data.

This TSAP assumes familiarity with the Clinical Trial Protocol (CTP), including Protocol Amendments. In particular, the TSAP is based on the planned analysis specification as written in CTP Section 7 “Statistical Methods and Determination of Sample Size”. Therefore, TSAP readers may consult the CTP for more background information on the study, e.g., on study objectives, study design and population, treatments, definition of measurements and variables, planning of sample size, randomisation.

This is a randomised, double-blind, placebo-controlled, parallel group trial evaluating safety, tolerability, pharmacodynamics and pharmacokinetics of BI 1291583 5 mg qd over 12 weeks versus placebo in adult patients with cystic fibrosis Bronchiectasis (ClairaflyTM). 

Unless otherwise noted, SAS® Version 9.4 will be used for all analyses.

## **4. CHANGES IN THE PLANNED ANALYSIS OF THE STUDY**

### **4.2 CLARIFICATION**

The terms 'subject' and 'patient' will be used interchangeably in this document.

## **5. ENDPOINTS**

### **5.1 PRIMARY ENDPOINT(S)**

The primary endpoint is the occurrence of any treatment-emergent adverse event (TEAE), up to 16 weeks after first drug administration. Details on the concept of TEAE are described in [Section 7.8.1](#).

### **5.2 SECONDARY ENDPOINT(S)**

#### **5.2.1 Key secondary endpoint(s)**

This section is not applicable as no key secondary endpoint has been specified in the protocol.

#### **5.2.2 Secondary endpoint(s)**

5.2.2.1 Relative change from baseline in neutrophil elastase (NE) activity in sputum at Week 8 after first drug administration

This endpoint will be derived based on NE activity levels at pre-specified visits over 12 weeks using log10 transformed values. The relative change from baseline in sputum NE at Week 8 will be estimated as described in [Section 7.5.2.1](#).

5.2.2.2 Pharmacokinetic endpoints

The following pharmacokinetic endpoints are assessed for BI 1291583 5 mg only.

- AUC $\tau$ : AUC (area under the curve) over a dosing interval for the first dose
- Cmax: maximum concentration for the first dose
- AUC $\tau$ ,ss: AUC $\tau$  at steady state after multiple dosing of BI 1291583 5 mg qd
- Cmax,ss: Cmax at steady state after multiple dosing of BI 1291583 5 mg qd

Proprietary confidential information © 2024 Boehringer Ingelheim International GmbH or one or more of its affiliated companies.

Pharmacokinetic endpoints from the population PK analysis and/or Population PK/PD analysis will be defined in the Population PK Analysis Plan. Refer to Section 7.2.4.2 of the CTP for details of the analyses of the pharmacokinetic endpoints.

[figure not shown]

**Boehringer Ingelheim**  
**TRIAL STATISTICAL ANALYSIS PLAN**  
**1397-0013**

**Page 12 of 37**

**c44359225-01**

Proprietary confidential information © 2024 Boehringer Ingelheim International GmbH or one or more of its affiliated companies.

## 6. GENERAL ANALYSIS DEFINITIONS

### 6.1 TREATMENT(S)

#### 6.1.1 Analysis phases

For safety analyses, data collected between first drug intake up to the end of residual effect period (REP) will be considered as “on-treatment” period for the evaluation.

Table 6.1.1: 1 Analysis phases

Study analysis phase	Label	Start (included)	End (excluded)
Screening	Screening	Date of informed consent at 12 a.m.	Date/time of first drug administration
Treatment	Placebo BI 5 mg respectively	Date/time of first administration of study drug	12:00 a.m. on day after last drug administration, or 12:00 a.m. on day after last contact date (whichever occurs first)
Residual effect period	Residual effect period	12:00 a.m. on day after last administration of study drug	12:00 a.m. on day after last administration of study drug + REP (28 days)
Follow-up 	Follow-up	12:00 a.m. on day after last administration of study drug + REP (28 days)	12:00 a.m. on day after last contact date

 This phase exists only in those subjects whose last contact date is more than 28 days after last trial drug administration.

#### 6.1.2 Treatment grouping

All analyses will be conducted on the TS, with subjects grouped by randomised treatment assignment.

Subjects that received wrongly assigned kits during study will be reviewed shortly after unblinding and any decision to assign these subjects to different treatment arms compared to the above rules will be documented in the decision log (9.2).

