7.2 PLANNED ANALYSES

7.2.1 General considerations

The following analysis sets will be defined for statistical analyses:

- Screening set (SCS): This patient set includes all patients who signed informed consent. The SCS will be used for the analyses of patient disposition.
- Randomised set (RS): This patient set includes all randomised patients. The RS will be used for the analyses of patient disposition.
- Treated set (TS): This patient set includes all randomised patients who received at least one dose of trial medication. The TS is the main analysis set for the efficacy analyses, the safety analyses as well as for demographics and baseline characteristics and protocol deviations.
- Pharmacokinetic set (PKS): This patient set includes all patients from the TS who provided at least one post-dose plasma BI 1291583 concentration that was not excluded due to a protocol deviation relevant to the evaluation of PK, or due to PK non-evaluability.

For all analyses, patients will be analysed according to planned treatment group. In case of patients receiving the wrong medication unintentionally (i.e., different to their planned treatment), the impact to study outcomes will be assessed with details specified in the TSAP.

Adherence to the protocol will be assessed by the trial team. Important protocol deviation (iPD) categories (including violations of the key inclusion and exclusion criteria, incorrect medication taken and any other deviations of the protocol deemed important) will be specified in the Protocol Deviation Domain.

Protocol deviations will be identified no later than in the Report Planning Meeting, and the iPD categories will be updated as needed. All decisions concerning important protocol deviations will be made prior to database lock.

Further analysis sets will be defined in the TSAP, if needed.

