## **7.8 SAFETY ANALYSIS**

All safety analyses will be presented by randomised treatment and overall total, based on the TS.

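### SAP 6.1.2 allows patients with wrongly assigned kits to be moved to another arm after unblinding, with no criterion in the SAP text, although the protocol and SAP 7.8 group patients as planned or randomised

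*SAP*

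**What the plan says.** SAP 6.1.2 opens with a clear default: "All analyses will be conducted on the TS, with subjects grouped by randomised treatment assignment". The next sentence makes an exception: patients given kits in error "will be reviewed shortly after unblinding and any decision to assign these subjects to different treatment arms" is to be entered in a log. The section does not say what would justify a different arm or who decides. Nor does it require the as-randomised result to be shown alongside.

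The other relevant places are:

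- **SAP 7.8:** "All safety analyses will be presented by randomised treatment and overall total, based on the TS". The exception is not repeated.
- **SAP 7.4 and 7.4.1:** the primary analysis is the number and percentage of patients with at least one TEAE, taken from the safety analysis.
- **SAP 8:** codes are released after the last patient's follow-up visit, once data are entered and cleaned.
- **SAP 6.3:** the intercurrent events handled as important deviations are confirmed before unblinding.
- **Protocol 7.2.1:** "For all analyses, patients will be analysed according to planned treatment group". If a patient unintentionally receives the wrong medication, "the impact to study outcomes will be assessed with details specified in the TSAP". Taking incorrect medication is named as an important-deviation category, and "All decisions concerning important protocol deviations will be made prior to database lock".
- **Protocol 2.1.1:** treatment effects are estimated as randomised.

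**The concern.** The protocol hands the SAP one task for wrong medication: to give the details of an impact assessment. It does not mention changing a patient's arm. The SAP gives no such details and instead opens a case-by-case choice of arm, made when codes and outcomes are both available. A decision log makes the choice traceable but does not limit it.

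The choice is not always obvious. Protocol 4.1.4 has one tablet a day for 12 weeks from bottles of 20, so a patient needs at least five bottles (84 / 20 = 4.2, rounded up). A single wrong bottle gives mixed exposure, and first kit, most doses or any active dose could each be defended. At stake is the primary safety table, in which one arm has only 8 patients.

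**Working it through.** The plan states no figure for this point, so there is none to reproduce. The check compares the texts and then measures how much one reassignment can move the primary table.

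**Step 1. Texts side by side.**

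| Place | Grouping | Exception for wrong kits |
|---|---|---|
| Protocol 2.1.1 | As randomised | None |
| Protocol 7.2.1 | Planned group, all analyses | Impact assessment, details left to the SAP |
| SAP 7.8 | Randomised treatment, all safety | None |
| SAP 6.1.2 | Randomised treatment | Another arm possible, decided after unblinding |

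Only SAP 6.1.2 allows a change of arm.

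**Step 2. Inputs.** Protocol 7.5 gives 16 active and 8 placebo patients, consistent with 2:1 allocation of 24 (24 × 2/3 = 16; 24 × 1/3 = 8). Let a and p be the numbers with at least one TEAE in the active and placebo arms. The documents give neither these counts nor an expected number of kit errors, so all possible counts are considered.

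**Step 3. Effect of moving one patient.** The risk difference is a/16 − p/8. Its change is:

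- Placebo to active, patient with a TEAE: (a+1)/17 − (p−1)/7 − (a/16 − p/8) = (16−a)/272 + (8−p)/56, never negative.
- Placebo to active, patient without a TEAE: a/17 − p/7 − (a/16 − p/8) = −a/272 − p/56, never positive.
- Active to placebo, patient with a TEAE: (a−1)/15 − (p+1)/9 − (a/16 − p/8) = −(16−a)/240 − (8−p)/72, never positive.
- Active to placebo, patient without a TEAE: a/15 − p/9 − (a/16 − p/8) = a/240 + p/72, never negative.

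For a given direction of move, the sign therefore depends only on whether that patient had a TEAE.

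**Step 4. Largest shifts.**

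- Placebo to active: with a = 0 and p = 1, 16/272 + 7/56 = 0.0588 + 0.1250 = 0.184, or 18.4 points.
- Active to placebo: with a = 15 and p = 8, 15/240 + 8/72 = 0.0625 + 0.1111 = 0.174, or 17.4 points.
- Two patients moved: up to 36.1 and 32.5 points respectively, from enumerating all counts.

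**Step 5. Mid-range illustrations (assumed counts), one placebo patient moved to active.**

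| Start | Patient had a TEAE | Patient had none |
|---|---|---|
| 8/16 vs 4/8 (difference 0) | 9/17 vs 3/7 = 52.9% vs 42.9%, +10.1 points | 8/17 vs 4/7 = 47.1% vs 57.1%, −10.1 points |
| 10/16 vs 5/8 (difference 0) | 11/17 vs 4/7 = 64.7% vs 57.1%, +7.6 points | 10/17 vs 5/7 = 58.8% vs 71.4%, −12.6 points |

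**Step 6. Under the fix.** If randomised grouping is kept, a post-unblinding decision shifts the main table by 0.

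**The case against.** The case against has real force.

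- **The main grouping is fixed.** The default is as randomised, and discretion reaches only patients with wrong kits. A reader might infer that the SAP has no grouping rule at all; it does. SAP 6.2 also refers to deviation specifications in the trial master file, which cannot be seen here and might hold a criterion. The supportable statement is that the SAP text contains none.
- **The timing has a reason.** Protocol 4.1.5.1 keeps kit lists restricted while the team is blinded, so the team may not know before unblinding whether a wrong kit held the other treatment. That stands. It justifies applying a rule at that point, not choosing one then.
- **A breach of the pre-lock rule is not shown.** A reader might infer that a review after unblinding violates the protocol's timing for deviation decisions. SAP 8 does not place unblinding relative to database lock, and classifying a deviation is separate from deciding how to group the patient.
- **The percentage points are not a measure of bias.** A fixed rule by treatment received could move the same patient and give the same shift. The figures show how much one move matters. The bias arises because the move can be chosen with the outcome known.
- **As-received grouping should not simply replace the default.** A reader might infer that the main safety table ought to be by treatment received. Protocol 7.2.1 and 2.1.1 choose otherwise, so that would change a protocol-level decision.
- **The analysis is descriptive.** Protocol 7.1 has no confirmatory testing, so no error rate is affected.

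None of this supplies an advance criterion or reconciles SAP 6.1.2 with the other three sections.

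**Conclusion.** The point holds in a narrow form. SAP 6.1.2 permits a change of arm after unblinding with no criterion in its text and only a log as control, and this is inconsistent with Protocol 7.2.1, Protocol 2.1.1 and SAP 7.8. One such move can change the TEAE risk difference by at most 18.4 points (placebo to active) or 17.4 points (active to placebo), and by roughly 8 to 13 points in the mid-range illustrations.

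These sizes assume the planned 16 and 8 patients are treated and that at least one kit error occurs; with no error the effect is nil. They describe side-by-side proportions in an exploratory trial, not a test result. The issue is unlikely to arise but would touch the primary endpoint, and it is cheap to close, so it should be corrected before unblinding.

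**What to change.** Amend SAP 6.1.2 before unblinding:

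1. Delete the option to place patients in a different arm.
2. State that randomised grouping is the main analysis for all endpoints, in line with SAP 7.8 and Protocol 7.2.1 and 2.1.1.
3. Pre-specify one supportive TEAE table by treatment received, produced only if a kit error occurs. Write the definition of treatment received now (for example, active if any active tablet was taken) and apply it mechanically once kit contents are known. Writing the definition needs no access to the codes.
4. Keep the decision log to record the kit errors found and how the definition was applied.

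Item 3 also supplies the impact assessment that Protocol 7.2.1 leaves to the SAP. The cost is a few sentences of SAP wording and at most one extra table. No protocol amendment is needed, because the main grouping stays as the protocol has it.

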## 6.2 IMPORTANT PROTOCOL DEVIATIONS

Protocol deviations identified during the trial will be discussed at the clinical quality monitoring meetings or at the report planning meeting prior to DBL. Handling of important protocol deviations (iPDs) in analysis is included in the DV domain specifications and stored within the Trial Master File (TMF) in Electronic Document Management System (EDMS). An overview of the number of patients with iPDs will be presented to demonstrate the adherence to the CTP.

The process of identification of iPDS is according to “Identify and Manage Important Protocol Deviations (iPD)” ([9.3](#)).

### **6.3 INTERCURRENT EVENTS**

The expected intercurrent events (ICE) of interest are:

1. Treatment discontinuation
2. Initiation of macrolides for chronic use during trial
3. Initiation of cyclic doses of antibiotic treatment for chronic use during trial
4. Initiation or change of CFTR-MT during the trial

ICE #1 will be collected as disposition data in eCRF; ICE #2, #3 and #4 will be reported as iPDS and confirmed prior to unblinding. The number and percentage of patients reporting each type of intercurrent event will be summarized by treatment group.

In general, analysis strategies to address ICEs that reflect the treatment effect estimation are following ICH E9 (R1) ([9.4](#)). The primary objective analysis will be based on while-on-treatment strategy, where data collected up to the end of residual effect period (REP) will be included for the primary endpoint analysis.

For secondary objective analysis, ICEs will be handled using the treatment policy strategy, i.e., data collected regardless of intercurrent events will be used when analyzing secondary endpoints.

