7.2.2 Handling of Intercurrent Events

The expected intercurrent events (ICEs) of interest in this trial are:

[figure not shown]
- Treatment discontinuation
- Initiation of macrolides during trial
- Start of cyclic doses of antibiotic treatment during the trial
- Initiation or Change of CFTR-MT during the trial

For the primary objective, intercurrent events will be handled by using the while-on-treatment strategy, as defined in ICH E9(R1) [[R21-0743](#)]. Measurements, taken prior to the intercurrent event, will be used to assess treatment effect.

For the secondary objective, intercurrent events will be handled by using the treatment policy strategy, as defined in ICH E9(R1). Use of the “treatment policy” approach disregards the intercurrent event and uses measurements regardless of the occurrence of an intercurrent event. Additional details regarding intercurrent event handling strategy will be described in the TSAP.

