## **6.7 BASELINE, TIME WINDOWS AND CALCULATED VISITS**

For all parameters (except for biomarkers), baseline is defined as the last non-missing value prior to first administration of trial medication, or on the same date of first drug administration, if assessment times are not collected (e.g., vital signs, laboratory tests).

For specific assessments, multiple measurements are planned prior to first drug intake (e.g., at Visit 1 or 2). To derive the baseline, specific rules will apply as shown in [Table 6.7: 1](#).

According to CTP Section 5.4.1.3.2 Sputum sample collection at site, if sputum samples do not meet the sputum collection criteria as defined in the ISF/Lab Manual, it is generally possible that the patient returns the next day to provide the sputum sample. Baseline sputum measurement could be on or prior to the first drug administration + 1 day.

Table 6.7: 1 Derivation of baseline for assessments with multiple measurements prior to first drug administration

Parameter	Baseline value derivation
Biomarkers based on sputum	Mean of all available valid measurements collected up to date of first study drug administration + 1 day
Murray sputum colour chart	Last valid measurement collected up to date of first study drug administration + 1 day
NEATstik®	Mean of all available valid samples collected up to date of first study drug administration + 1 day

Measurements taken after first administration of trial treatment will be considered either on- or off-treatment values based on the definition in [Table 6.1.1: 1](#). Visit windowing will be performed as described in the tables below, in order to assign data to the relevant study visit based on the actual day of the assessment. Data will be analyzed using the re-calculated visits in the statistical tables. However, in the listings, all visits performed will be displayed (even if outside time-window), along with the re-calculated visit. The date of first treatment intake will be used as Study Day 1 for the time windowing. If more than one value is available within one time window the one which is closest to the planned time/day is used for analysis. In case two values are equidistant from the planned time/day, then the last one will be picked.

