Analysis of AE data (including findings in 12-lead ECG assessments or physical examinations), potentially clinically significant abnormal laboratory values, concomitant medication or non-drug therapies will not be based on visits and thus no assignment to time windows is necessary. For this type of data, a safety analysis ‘on-treatment’ concept will be used depending on their actual onset dates.

Table 6.7: 2 Time windows for assignment of safety assessment – laboratory

[figure not shown]
Visit number (CTP)	Visit label (analysis)	Planned Day	Time window [days]		
			Window per CTP	Start (analysis)	End (analysis)
V1	Screening	-42	≥7d prior to V2	All pre-baseline measurements	
V2	Baseline	1	± 0	NA	Date/time of first administration of study drug
V3	Week 1	8	± 3	Start of on-treatment phase 	18
V4	Week 4	29	± 3	19	43
V5	Week 8	57	± 3	44	71
V6	Week 12	85	± 3	72	End of on-treatment phase 
EoS	Follow-up	113	+ 7	All post-treatment measurements after last drug intake + REP	

 As defined in [table 6.1.1: 1](#).

Table 6.7: 3 Time windows for assignment of biomarkers assessed in sputum

Visit number (CTP)	Visit label (analysis)	Planned Day	Time window [days]		
			Window per CTP	Start (analysis)	End (analysis)
V1	Screening	-42	≥7d prior to V2	All pre-baseline measurements	
V2	Baseline	1	± 0	NA	Date/time of first administration of study drug
V3	Week 1	8	± 3	Start of on-treatment phase 	18
V4	Week 4	29	± 3	19	43
V5	Week 8	57	± 3	44	71
V6	Week 12	85	± 3	72	Last drug administration
EoS	Safety Follow-up	Last drug administration + 28		All measurements after last drug administration + 1	All measurements before last drug administration + 36

 As defined in [table 6.1.1: 1](#).

Proprietary confidential information © 2024 Boehringer Ingelheim International GmbH or one or more of its affiliated companies.

For all variables with a sparse sampling schedule that does not match the schedules in the above tables, the screening, baseline and follow-up phase will follow the same rules, while the start and end days of the on-treatment time windows will be equidistant from the planned visit day.

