### **% inhibition analyses**

The assessment of NE activity will further comprise the analysis of the % inhibition of NE activity. For the purpose of descriptive analysis, for each time point including baseline, % inhibition will be calculated as:

$$NE \ inhibition_t = \frac{NE \ activity_{baseline} - NE \ activity_t}{NE \ activity_{baseline}} \times 100$$

Descriptive statistics for absolute % inhibition by timepoint and treatment group will be presented. Maximum % inhibition (on patient level during the trial) will be summarized by treatment group. The median % inhibition of NE activity per treatment group over time will be plotted. All timepoints will be taken into account, analysis windows will be applied to the % inhibition of NE activity.

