### **Change from baseline analyses**

Change from baseline in log10-transformed NE activity in sputum up to Week 12 after first drug administration will be analysed by descriptive statistics and graphical representations across all visits. Descriptive statistics of change from baseline will be presented by timepoint and treatment group.

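### SAP Table 6.7:3 closes the Week 12 sputum window at the last dose, so off-drug NE values from Day 72 on are dropped and a completer's next-day EOT sample falls in no row

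*SAP*

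**What the plan says.** Treatment discontinuation is the first intercurrent event listed in SAP 6.3, and for the secondary objective the rule is that "data collected regardless of intercurrent events will be used when analyzing secondary endpoints". Protocol 7.2.2 describes the same strategy as one that "disregards the intercurrent event and uses measurements regardless of the occurrence of an intercurrent event". SAP 5.2.2.1 derives the NE endpoint from the planned visits over 12 weeks, with Week 8 as the named timepoint.

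SAP 6.7 uses windows, counted from first intake as Day 1, to "assign data to the relevant study visit based on the actual day of the assessment". For sputum biomarkers, Table 6.7:3 gives:

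- Week 8: Day 44 to Day 71, with no condition on treatment status.
- Week 12: Day 72 to the last dose.
- Safety Follow-up: from "All measurements after last drug administration + 1" to "All measurements before last drug administration + 36".

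The only visible selection rule is "If more than one value is available within one time window the one which is closest to the planned time/day is used for analysis", with the later value taken if two are equally close.

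These windows decide what is summarised under SAP 7.5.2.1. For percent inhibition, "All timepoints will be taken into account, analysis windows will be applied to the % inhibition of NE activity". The other summary is "Change from baseline in log10-transformed NE activity in sputum up to Week 12 after first drug administration", by timepoint and treatment group.

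Three protocol rules determine which samples exist. The last dose is given at EOT (4.1.4). A patient who cannot produce sputum on the visit day may come back the following day (5.4.1.3.2). A patient who stops early has a prompt EOT visit and an EOS visit 28 (+7) days after it (Flow Chart, footnote 1), and sputum is scheduled at both.

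**The concern.** The Week 12 row contains an on-drug condition that the declared strategy rules out. Under treatment policy, a patient who stopped early and gave sputum around Day 85 belongs in the Week 12 summary. Under the table, that value can appear only in Safety Follow-up or nowhere. The Week 12 summary then describes patients still on drug, while SAP 6.3 says otherwise.

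The second gap reaches patients who complete treatment. SAP 6.7 cites the next-day return and extends the baseline window by one day to allow for it. The Week 12 row has no such extension, and Follow-up starts one day too late to catch the sample. A valid end-of-treatment sample would then appear in listings but in no by-visit table.

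**Working it through.** Let L be the study day of the last dose and S the study day of the sample. A sample is off drug when S > L. The rows of Table 6.7:3, read in whole days, are:

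- Week 8: 44 ≤ S ≤ 71
- Week 12: 72 ≤ S ≤ L
- Safety Follow-up: L + 2 ≤ S ≤ L + 35

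**Off-drug samples and Week 12.** Week 12 needs S ≤ L and off drug means S > L, so no off-drug sample can qualify. If L ≤ 71 the window is empty. As a check, L = 1 to 71 with S = 72 to 85 gives 71 × 14 = 994 day combinations. None is in Week 12: 398 are in Follow-up only and 596 are in no row.

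**Scheduled visits that meet this.** Assume EOT on the day of the last dose, so EOS falls on L + 28 to L + 35. The number of the 8 allowed EOS days that fall in Days 72-99 is:

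- EOT on Days 37-43: 1 rising to 7
- EOT on Days 44-64: all 8
- EOT on Days 65-71: 7 falling to 1

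For example, with last dose and EOT on Day 50, EOS may fall on Days 78-85. A sample on Day 85 is on the planned Week 12 day, yet it is 85 − 50 = 35 days off drug and counts in Follow-up only.

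**Completer with a next-day sample.** Take L = 85 and S = 86. Week 12 needs 86 ≤ 85, which fails. Follow-up needs 86 ≥ 87, which fails. The sample is in no row.

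**A fixed end for Week 12.** The table's own pattern is planned day + 14: 29 + 14 = 43 for Week 4 and 57 + 14 = 71 for Week 8. For Week 12 this gives 85 + 14 = 99, which is also the midpoint (85 + 113)/2. It separates the completers' visits. The latest in-window EOT is Day 88, so a next-day sample is Day 89 (inside). The earliest EOS, 28 days after an EOT on Day 82, is Day 110 (outside).

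**Week 8.** Take L = 30 and an EOS sample on S = 58. Week 8 holds (44 ≤ 58 ≤ 71) and so does Follow-up (32 ≤ 58 ≤ 65). In general the two rows overlap for S in 44-71 at 2 to 35 days off drug, which occurs for L = 9 to 69. At 36 or more days off drug the sample meets Week 8 only.

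**Illustration of size, not an estimate.** The documents give no stopping rate, so I assume 1 or 2 stoppers among 16 active patients. I take an on-drug reduction of 90% (a scenario in protocol Table 7.5:1) and SD 2.15 on the log10 scale (the table's stated assumption).

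| Mean log10 change, back-transformed | 1 stopper | 2 stoppers |
|---|---|---|
| Stoppers excluded | 90% | 90% |
| Included, fully reversed | 1 − 10^(−15/16) = 88.5% | 1 − 10^(−14/16) = 86.7% |
| Included, half reversed on log10 | 1 − 10^(−15.5/16) = 89.3% | 1 − 10^(−15/16) = 88.5% |

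Full reversal shifts the mean by 1/16 = 0.0625 or 2/16 = 0.125 log10. With SE = 2.15/√16 = 0.5375, that is 0.12 or 0.23 SE.

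**The case against.** The strongest defence is that Week 12 is not the declared endpoint. The secondary endpoint is Week 8, and in the visible plan each visit is summarised descriptively, so nothing in the Week 12 row changes the Week 8 result. Closing Week 12 at the last dose also keeps washout values apart from on-drug values. The first part stands and is why the point is minor. The second does not, because SAP 6.3 and protocol 7.2.2 chose treatment policy for this objective without exempting Week 12. A separate Follow-up summary can show washout values without removing them from Week 12.

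On the next-day sample, the one-day offset at the start of Follow-up was probably meant to leave that day with EOT. That is plausible, but the Week 12 row does not say it. The case is rare, since the next-day return is a fallback and a home sample from the visit morning may be available as backup.

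For Week 8, a reader might infer from the overlap that off-drug samples are taken out of the endpoint, so that it departs from treatment policy. The documents do not support this. The Week 8 row carries no on-drug condition, windowing runs from first intake, SAP 6.3 keeps off-drug data, and nothing visible makes the rows exclusive or gives Follow-up precedence. Following the visible text puts the sample in Week 8.

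Part of the SAP around section 6.7 is not shown, so a precedence rule may exist in removed text. For Week 8 that could settle the matter. For Week 12 it would have to override a row that is stated.

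**Conclusion.** The Week 12 limb holds. As written, the row excludes every off-drug sputum NE value from Day 72 on, contrary to the declared treatment policy, and it leaves a completer's permitted next-day EOT sample in no analysis row. The Week 8 overlap is real on a literal reading, but it calls only for a clarifying sentence.

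Severity is minor. The effect is confined to early stoppers and next-day EOT samples in a descriptive secondary analysis. Its size cannot be computed without a stopping rate, and the illustrated shifts rest on an assumed number of stoppers. Counts of day combinations, such as the 994 above, show that the exclusion is complete. They give equal weight to days on which no sample is scheduled, so they say nothing about how many patients are affected.

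The verdict reads the Week 12 end as a calendar day. If it were a clock time, a sputum sample taken after dosing at EOT, which protocol 6.1 allows, would also fall outside. The row does not say so, and I do not rely on it.

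**What to change.** In Table 6.7:3, end the Week 12 sputum window at a fixed study day whatever the treatment status, for example Day 99. The existing closest-to-planned-day rule then chooses if a patient has more than one value. Allow off-drug samples in the visit windows to be shown also in a separate Safety Follow-up summary, with a footnote that a sample may appear in both.

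Add one sentence that a Day 44-71 sample counts in Week 8 even if it also meets the Follow-up row. It could cover the Week 1 and Week 4 rows too, which overlap with Follow-up in the same way. If removed text already gives the rule, a cross-reference in the table is enough.

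The cost is one table edit, one sentence and one footnote, made before treatment information is released. No new data and no protocol amendment are needed. The Week 12 reduction may look slightly smaller once off-drug values are included, which is what treatment policy implies.
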